8.4. Subgroup Analyses for Combined Study Analysis

For the combined study analysis, subgroup analyses for the primary and secondary endpoints will be provided by:

1. Sex

2. Race (white vs. other)
3. Baseline event rate (≥ 2 events/month vs. < 2 events/month)
4. Age group (12 - 17, 18 to 64, ≥ 65 years)
5. Region (North America vs. Japan vs. rest of world)
6. Weight ($<$ median vs. \geq median)
7. BMI (18.5 to 24.9 kg/m² vs. 25 to 29.9 kg/m² vs. ≥ 30 kg/m²)
8. Prior androgen use (yes vs. no)

A summary of TEAEs by age group will also be provided.

8.5. Multiple Comparisons and Multiplicity

There are 4 endpoints being tested in the combined analysis, the primary endpoint and 3 secondary endpoints. For each endpoint, there are 2 potential doses to be tested. The Type I error rate will be controlled at the study level by using a combination of hierarchical testing and the Hochberg procedure. The 4 endpoints will be tested in a hierarchical fashion and the 2 doses will be tested using the Hochberg step-up procedure at each level of the hierarchy to which both doses progress through the hierarchy.

The first endpoint to be tested is the primary endpoint, the rate of expert-confirmed angioedema events during dosing in the entire 24-week treatment period of Part 1. Using the Hochberg step-up procedure, each of the 2 doses will be tested at the $\alpha = 0.05$ level, comparing active treatment to placebo. If the maximum of the 2 p-values is ≤ 0.05 , the null hypotheses of no difference between the rate of angioedema events for subjects on active and placebo treatment will be rejected for both doses and testing will proceed to the next endpoint in the hierarchy with $\alpha = 0.05$. If the maximum of the 2 p-values is > 0.05 but the minimum of the 2 p-values is < 0.025 , the null hypothesis for the dose with $p < 0.025$ will be rejected and testing for that dose only will proceed to the next endpoint in the hierarchy with $\alpha = 0.025$. Otherwise, the null hypotheses for both doses will not be rejected, testing will stop, and the hypothesis for the next endpoint in the hierarchy will not be tested.

The first, second, third, and fourth endpoints in the hierarchy are:

1. The rate of expert-confirmed HAE events during dosing in the entire 24-week treatment period (Day 1 to Day 168)
2. Number and proportion of days with angioedema symptoms through 24 weeks
3. Rate of expert-confirmed HAE events during dosing in the effective dosing period (beginning on Day 8 through 24 weeks)
4. Change from baseline in AE-QoL at Week 24 (total score)

The process described above will be continued for each endpoint in the hierarchy until either all 4 endpoints have been tested or testing has stopped due to non-rejection of the null hypotheses for both doses for endpoints earlier in the hierarchy. At each level of the hierarchy, the Hochberg step-up procedure is used to control Type I error rates if 2 doses are to be tested. Otherwise, if only one dose is being tested, the single test is conducted with $\alpha = 0.025$.

The sample size considered feasible for enrollment in Japan has limited statistical power. Therefore, a supplemental statistical analysis will be conducted in the same manner as above using the combined data from Studies 301 and 302. The combined rate of HAE events will utilize investigator-confirmed attacks from Study 302 and expert-confirmed events from Study 301.

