5.3.1. Summary of Study BCX7353-302

Study BCX7353-302 is a Phase 3, randomized, double-blind, placebo-controlled, parallel-group, 3-part study in subjects with Type 1 or 2 HAE. The primary objective of the study was to determine the efficacy of prophylactic BCX7353 110 and 150 mg administered orally once daily (QD) for 24 weeks (Part 1) compared to placebo in subjects with HAE.

In Part 2, all subjects receive active treatment with BCX7353 from Weeks 25 through 48, and Part 3 of the study extends treatment with BCX7353 through 96 weeks. Results for Part 1 are summarized herein; Parts 2 and 3 of the study are ongoing.

Overall, a total of 160 subjects were screened, 121 subjects were randomized (stratified by baseline attack rate, < 2 vs. ≥ 2 per 28 days), and 120 randomized subjects (99%) were treated. Of these, 108 subjects completed 24 weeks of study drug dosing in Part 1: 37 of 40 BCX7353 150 mg subjects (93%), 37 of 41 BCX7353 110 mg subjects (90%), and 34 of 39 placebo subjects (85%).

The mean baseline rate was 2.98 attacks per month. The majority of subjects (70%) had ≥ 2 attacks per month at baseline, and the attack frequency was generally well distributed across the 3 treatment groups.

The primary efficacy endpoint was the rate of investigator-confirmed HAE attacks during dosing in the entire 24-week treatment period. This study achieved its primary endpoint for both dose levels, with the 150 and 110 mg doses reducing HAE attacks by 44% ($p < 0.001$) and 30% ($p = 0.024$), respectively, vs. placebo. The attack rate per 28 days over the 24-week Part 1 dosing period was 1.31 for BCX7353 150 mg subjects, 1.65 for BCX7353 110 mg subjects, and 2.35 for placebo subjects. These results were supported by sensitivity analyses and were generally consistent in subgroup analyses. Effects of BCX7353 in reducing attack rate were evident in the first 4 weeks and stable over the entire 24-week duration of Part 1.

Secondary endpoints (change from baseline in the angioedema quality of life questionnaire [AE QoL], number and proportion of days with angioedema symptoms, and rate of investigator-confirmed HAE attacks during the effective dosing period [beginning on Day 8 through Week 24]) were analyzed using hierarchical testing. Results for the first secondary endpoint, AE QoL, were not statistically significant vs. placebo for either treatment group; therefore, inferential statistical testing was not performed on the descending secondary efficacy endpoints.

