13.1.2. Secondary Hypotheses

For each dose separately, the following secondary hypotheses will be tested in a combined analysis of the current study with Study BCX7353-302:

1. Proportion of days with angioedema symptoms

- H_0 : $\beta=0$; active treatment does not have a differential effect on the proportion of days with angioedema symptoms over the entire treatment period
- H_A : $\beta\neq 0$; active treatment does have a differential effect on the proportion of days with angioedema symptoms over the entire treatment period

where β is the parameter representing treatment effect for the dose of interest in an analysis of covariance (ANCOVA) model.

2. Rate of investigator- or expert-confirmed angioedema events during the effective treatment period (beginning on Day 8 through 24 weeks)

- H_0 : $R_A=R_P$; active treatment does not have a differential effect on the rate of expert-confirmed angioedema events during the effective treatment period
- H_A : $R_A\neq R_P$; active treatment does have a differential effect on the rate of expert-confirmed angioedema events during the effective treatment period

where R_A is the monthly angioedema event rate for active treatment and R_P is the monthly angioedema event rate for placebo treatment during the effective treatment period.

3. AE-QoL

- H_0 : $\beta=0$; active treatment does not have a differential effect on the change from baseline AE-QoL at Week 24
- H_A : $\beta\neq 0$; active treatment does have a differential effect on the change from baseline AE-QoL at Week 24

where β is the parameter representing treatment effect for the dose of interest in a mixed effect model for repeated measurements (MMRM).

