13.2.2. Sample Size for the Combined Analysis of Studies BCX7353-301 and BCX7353-302

Assuming a weekly angioedema event rate for placebo subject of 0.9 and a common SD of 0.50 angioedema events per week for BCX7353 and placebo, a sample size of 120 subjects (40 per treatment group: 8 from BCX7353-301 and 32 from BCX7353-302) will provide > 99% power to detect a $\geq 67\%$ angioedema event rate reduction (a treatment difference of 0.6 angioedema events per week) between each BCX7353 active dose and placebo, based on a 2-sided test at significance level of 0.05. To control for familywise type I error, the Hochberg step-up procedure will be used to adjust for the comparison of the active doses to placebo.

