8.7. Analysis of the Secondary Efficacy Endpoints

Analysis of the secondary efficacy endpoints will be conducted for the combined study.

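### The plan claims study-level Type I error control, but its rule for carrying a single dose down the hierarchy does not give strong 5% familywise control (worst case about 7.4%)

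*SAP*

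**What the plan says.** SAP 8.5 and protocol 13.1.3 set out the same procedure. The order is the event rate over the whole dosing period, days with symptoms, the event rate from Day 8, and AE-QoL at Week 24. At each level reached by both doses:

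- If the larger p-value is at most 0.05, both doses are rejected and both go on at 0.05.
- If the larger p-value exceeds 0.05 and the smaller is below 0.025, only the better dose is rejected, and "testing for that dose only will proceed to the next endpoint in the hierarchy", at 0.025.
- At later levels, "if only one dose is being tested, the single test is conducted with" alpha 0.025.

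Both sections say of this scheme: "The Type I error rate will be controlled at the study level by using a combination of hierarchical testing and the Hochberg procedure". Neither gives a percentage with that sentence. The 5% figure comes from protocol 13.1.1, where it is attached to the primary comparisons.

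The secondary tests belong mainly to the pooled data. Protocol 13.1.2 says that "the following secondary hypotheses will be tested in a combined analysis of the current study with Study BCX7353-302". SAP 8.7 says "Analysis of the secondary efficacy endpoints will be conducted for the combined study". SAP 8.5 ends by stating that "a supplemental statistical analysis will be conducted in the same manner as above using the combined data from Studies 301 and 302". The output lists in SAP 17.1 carry a hierarchical-testing table for Study 301 and another for the combined studies.

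A narrower statement appears in protocol 13.2.2 and SAP 4.3.2, where "the Hochberg step-up procedure will be used to adjust for the comparison of the active doses to placebo".

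**The concern.** Full Hochberg can use the whole 0.05 on the weaker dose. When that dose fails, nothing is left to hand on, yet the plan hands 0.025 to the dose that won. Two chances of a false claim can therefore exist side by side: one for the failing dose at 0.05, and one for the winning dose at a later endpoint at 0.025.

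At stake is how a secondary claim reached by one dose should be read, chiefly in the combined 301 and 302 analysis. A reader who relies on the stated control would take the whole set of claims from that analysis as protected at 5% across both doses.

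**Working it through.** **Inputs.** Alpha is 0.05, two-sided (protocol 13.1.1). There are four endpoints and two doses, with branch levels 0.05 and 0.025 (SAP 8.5, protocol 13.1.3). Allocation is 1:1:1 (protocol 9.3.2.1), so the shared placebo gives a correlation of about 0.5 between the two dose comparisons. Planned power is 61% for Study 301 alone and above 99% combined (protocol Table 6).

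**The plan's own figures first.** With 8 per group, a difference of 0.6 and an SD of 0.5, the noncentrality is 0.6 / (0.5 × √(2/8)) = 2.4. A two-sided t-test on 14 df then has 60.8% power, which matches 61%. With 40 per group the power is 99.96%, which matches the stated figure. For the primary step alone, Hochberg gives 5.0% when one dose is null and the other always wins, and about 4.8% when both are null at correlation 0.5. The 5% therefore holds for the two-dose primary comparison within one analysis.

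**Worst case over the hierarchy.** Let dose A be certain to win at some level where dose B is null, and let A be null at the next level.

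- False claim for B: p ≤ 0.05, probability 0.05.
- B fails (0.95) and A, tested alone, is falsely rejected at 0.025: 0.95 × 0.025 = 0.02375.
- Union under independence: 0.05 + 0.02375 = 0.07375, or 7.4%.

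With correlation r between the two null statistics, the union is 7.34% at r = 0.15, 7.27% at 0.25, 7.17% at 0.35 and 6.94% at 0.5.

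**Upper bound.** A dose can first be falsely claimed only at its first null endpoint. If the two doses have first nulls at different levels, a false claim for the earlier one needs p ≤ 0.05. A false claim for the other without it means that dose is being tested alone at 0.025. The sum is at most 0.075 under any dependence. If both first nulls are at the same level, the error lies inside one Hochberg step: at most 0.05 under the usual positive dependence, and 0.075 under any dependence.

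**How much under realistic power.** The full four-level rule was simulated with 1 million draws per cell. Assumptions: normal statistics; correlation 0.5 between doses, 0.8 among the first three endpoints, and 0, 0.3 or 0.6 with AE-QoL; equal single-test power wherever a dose works.

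| True state | Power of the effective dose(s) | Familywise error |
|---|---|---|
| 110 mg null; 150 mg works on endpoints 1–3, null on AE-QoL | about 100% | 7.2–7.4% |
| same | 99% | 6.7–7.2% |
| same | 90% | 5.8–6.3% |
| same | 80% | 5.4–5.6% |
| same | 61% (301-alone planning value) | 4.7–5.0% |
| same | 10–16% (301 alone at Study 302 rates) | 3.1–3.6% |
| 110 mg works on the primary only; 150 mg on 1–3 | 90% and 99% | 4.8–5.3% |
| Both work on 1–3, AE-QoL null | 61% / 90% / 99% | 2.0–2.3% / 2.8–3.9% / 4.1–4.7% |

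The 10–16% row uses the Study 302 rates in protocol 5.3.1: (2.35 − 1.31)/4 = 0.26 and (2.35 − 1.65)/4 = 0.175 events per week, with SD 0.5 and 8 per group. Under the global null the rule gives 4.8–5.0%, depending on the correlations.

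**Two data sets.** SAP 8.1 tests the primary endpoint on Study 301 and separately on the combined data, with no alpha split stated. If either result could support a claim, the error for the primary pair is 8.9–9.3%, assuming that 8 of 40 or 8 of 48 subjects per group come from Study 301. Any restated claim must therefore name the data set.

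**The case against.** The strongest reply is that the excess needs an unlikely truth. Protocol 5.3.1 reports of Study 302: "This study achieved its primary endpoint for both dose levels", with a 30% reduction for 110 mg. If both doses work on the first three endpoints, the error stays below 5%. If 110 mg works on the primary only, it is 4.8–5.3%. This stands and limits the practical weight. It does not make the sentence true, because strong control must hold in every configuration. The ingredients are also not fanciful: the combined analysis is planned at over 99% power, 110 mg was the weaker dose in Study 302, and AE-QoL was not significant there for either dose.

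A second reply is that the combined analysis is called supplemental and that most of its data were already reported. That also stands. The percentages are prospective properties of the rule, and neither 5% nor 7.4% is the operating error rate once most of the data are known. Even so, protocol 13.1.1 and 13.1.2 place the hypothesis tests on the combined data.

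A third is that study-level control is never defined as strong control at 5%. That is correct. It is the natural reading, but it is an inference.

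A reader might also go too far the other way and infer that each secondary test carries a 7.4% error, or that the primary result is inflated. The documents support neither. A lone-dose test is run at 0.025, and 7.4% is the chance of at least one false claim across both doses, most of it the 5.0% for the failing dose. The primary pair stays at 5% within each analysis.

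**Conclusion.** The control statement in SAP 8.5 and protocol 13.1.3 does not hold as written if it means strong 5% control over the four-endpoint, two-dose hierarchy. The worst case is about 7.4%, with a ceiling of 7.5% under any dependence. The excess is thus at most 2.5 percentage points and arises only through the lone-dose branch.

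The worst case and the ceiling follow directly from the rule. The intermediate figures rest on the assumed normal statistics and correlations, including the finding of no material excess at 61% power. The 5% for the primary pair relies on positive dependence between the dose comparisons, which a shared placebo provides, and applies to one data set at a time.

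The impact falls mainly on secondary claims in the combined analysis. No primary conclusion changes. The correction is worth making because it is cheap and the present statement promises more than the rule delivers.

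**What to change.** Replace the study-level sentence in SAP 8.5 and protocol 13.1.3 with:

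> Within each analysis (Study 301 alone; combined Studies 301 and 302) considered separately, the Hochberg procedure controls the familywise Type I error rate at 5% for the two dose-placebo comparisons of the primary endpoint; no adjustment is made for testing the primary endpoint in both analyses. Over the full four-endpoint hierarchy, the familywise error rate across both doses is not strongly controlled at 5% and can reach about 7.4% when one dose proceeds alone, although each lone-dose test is conducted at 0.025.

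This changes no test and costs no power.

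If the sponsor prefers a 5% claim over the whole hierarchy within an analysis, it should change the rule instead. The power figures below are per dose, with both doses effective on every endpoint and correlations 0.5 (doses), 0.8 (endpoints 1–3) and 0.3 (with AE-QoL).

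- **Go on only when both doses are rejected.** Maximum error is 5.0% and primary power is unchanged, but a lone winner gets no secondary tests. Power for the last endpoint falls from 27.3% to 20.2% at 61% single-test power, and from 73.3% to 66.3% at 90%.
- **Truncated Hochberg at the three non-final levels.** Reject both doses if the larger p is at most 0.0375, or one dose at 0.025, and pass 0.0125 to a lone dose. Since 0.0375 + 0.0125 = 0.05, control is kept. Primary power falls from 56.6% to 53.5% at 61%, and from 88.8% to 86.9% at 90%. Last-endpoint power falls from 27.3% to 22.9%, and from 73.3% to 69.4%.

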8.6. Analysis of the Primary Efficacy Endpoint

8.6.1. Primary Efficacy Analysis

The primary efficacy endpoint for Part 1 of the study is the rate of expert-confirmed HAE events during dosing in the entire 24-week dosing period during Part 1 (Day 1 to first dose of Part 2). The first dose in Part 2 is expected on Day 169. The primary efficacy analysis will be produced using the ITT population. The estimand will be based on data from subjects who are on study treatment and this analysis will not include data post treatment discontinuation.

The number of expert-confirmed HAE events for Part 1 will be analyzed by treatment group using appropriate descriptive statistics for the confirmed event rate (expressed as events/month) based on the 24-week dosing period or until study treatment discontinuation, if applicable. An additional summary of confirmed event rate by month, including CFB event rate and percentage CFB event rate by month, will be produced. The primary efficacy analysis will be conducted using Part 1 data and the primary efficacy endpoints will be summarized and listed by Part 1 treatment group.

The angioedema event rate and the treatment comparisons between each BCX7353 dose and placebo in the rate of expert-confirmed angioedema events during the entire dosing period will be analyzed using a negative binomial regression model. The number of expert-confirmed angioedema events will be included as the dependent variable, the treatment will be included as a fixed effect, the stratification variable (baseline monthly angioedema event rate) and study (for the combined study analysis) will be included as covariates, and the logarithm of duration on treatment will be included as an offset variable. The estimated rate of angioedema events for each treatment group, the treatment differences expressed as the angioedema event rate ratio (BCX7353 over placebo rate ratio), and their associated 95% confidence intervals (CIs) will be provided from the negative binomial regression model. Monthly will be defined as 28 days.

The percentage reduction from placebo will be calculated for each dose as:

$$\text{Percentage rate reduction} = (1 - \text{event rate ratio}) * 100 = (1 - \frac{R_A}{R_P}) * 100$$

Where R_P is the estimated event rate for Placebo treatment and R_A is the estimated event rate for Active treatment.

Example SAS pseudo-code for the negative binomial regression analysis is as follows:

```
proc genmod data = datasetname;  
  class trt01p /param=glm;  
  model ecevents = trt01p blatk /dist=negbin link=log offset=logdurtrt;  
run;
```

All statistical tests will be two-sided. Multiplicity adjustments for Part 1 analyses for the two dose groups are discussed in Section 8.5 along with handling of testing of multiple endpoints.

Plots of mean confirmed event rate by month and scatter plots of baseline event rate vs. 24-week event rate will be produced with a different color for each treatment. Plots of mean event rate per month will be updated to include the Part 2 data at the end of Part 2. Adjusted subject-reported event rate data per month will be plotted separately for Part 3, as Part 3 does not include expert confirmation of events. A scatterplot will be produced for the difference between the baseline confirmed event rate and the confirmed event rate for Part 1 vs. the baseline confirmed event rate. This scatterplot will also be produced by gender. A plot of confirmed events by study day for Part 1 will be presented for individual subjects by treatment group and will display the length of each event and will include the use of on-demand medication. A plot of individual event rates showing the baseline and the Part 1 confirmed event rate will be presented by treatment group. A plot of individual event rates showing the baseline and confirmed event rates for each month will be presented by treatment group.

The sample size considered feasible for enrollment in Japan has limited statistical power. Therefore, a supplemental statistical analysis will be conducted in the same manner as above using the combined monthly angioedema event rate (investigator-confirmed attacks in Study 302 and expert-confirmed events in Study 301) in the entire treatment period in the ITT population.

The relationship of selected baseline characteristics with the expert-confirmed events will be explored using an appropriate model-building method for Part 1.

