During the entire screening period (run-in period and the period after eligibility has been established during the run-in period but prior to randomization), angioedema events must meet the following stipulations to be counted in the baseline angioedema event rate calculation necessary for stratification, in addition to the expert confirmation:

- The angioedema events are unique, which is defined as an angioedema event that does not begin within 48 hours of the end of a previous angioedema event.
- The angioedema event must have either been treated, required medical attention, or be documented to cause functional impairment based on subject entry in the e-diary. Functional impairment is defined as the subject being unable to perform his or her daily activities without restriction (ie, subject records that he or she is at least slightly restricted in his or her daily activities during the angioedema event).
- The angioedema events must include symptoms of swelling. The expert will consider that symptoms of swelling, in addition to visible swelling, may also include symptoms in the oropharyngeal or abdominal regions that are indicative of internal swelling.

After randomization through the end of Part 2, the expert will use their judgment to confirm or reject a reported event as an angioedema event; however, all angioedema events must include symptoms of swelling. The expert will consider that symptoms of swelling, in addition to visible swelling, may also include symptoms in the oropharyngeal or abdominal regions that are indicative of internal swelling.

The selection of the independent expert(s) who will confirm or reject attacks will be made by the sponsor and may or may not be an investigator in the current study. Expert expectations for turn-around times of the event confirmation or rejection and how the event confirmation or rejection will be received by the investigator and site staff, especially in the period between screening and baseline, will be communicated separately.

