Qualifying angioedema events that are counted in the baseline angioedema event rate for stratification and those that are used to qualify a subject during the run-in period must be characterized as follows:

- The angioedema events must be unique, which is defined as an angioedema event that does not begin within 48 hours of the end of a previous angioedema event.
- The angioedema events must have either been treated, required medical attention, or have been documented to cause functional impairment, based on the subject's entry in the electronic diary (e-diary). Functional impairment is defined as the subject not being able to perform his or her daily activities without restriction (ie, subject records that he/she is at least slightly restricted in daily activities during an angioedema event).
- The angioedema events must include symptoms of swelling. The expert will consider that symptoms of swelling, in addition to visible swelling, may also include symptoms in the oropharyngeal or abdominal regions that are indicative of internal swelling.
- The angioedema events are otherwise confirmed by an independent expert to be angioedema events.

A study schematic can be found in [Figure 1](#).

Throughout the entire study, details of all angioedema events (attacks, symptoms, or swelling due to HAE) and compliance with study drug will be recorded in an e-diary. Angioedema events will be treated in accordance with the subject's normal standard of care. Within approximately 2 business days of the end of each angioedema event that occurs from the screening visit through the follow-up visit after Part 2, subjects will be contacted by the investigator (or appropriately trained designee) to discuss the clinical characteristics of the angioedema event, any questions on

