6.6.1. Baseline Event Rate

Enrollment into treatment groups is stratified by the baseline HAE event rate as determined by the IXRS system based on the number of events and duration of screening as input by the sites (≥ 2 events/month vs. < 2 events/month). For analysis purposes, the baseline event rate will be calculated from the diary data and expressed as events per month where 1 month = 28 days as follows:

$$\frac{\text{Number of HAE events meeting baseline criteria from Screening to First Dose Date/time} * 28}{\text{Date of First Dose} - \text{Screening Date} + 1}$$

Criteria that must be met for events to qualify for confirmation by the Investigator during the baseline period are provided in Section 4.1.

Baseline event rate will be included in statistical models as appropriate.

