6.7.2. Change from Baseline

CFB is calculated as (post-baseline result – baseline result). Percent CFB is calculated as ((change from baseline/baseline result) * 100).

If either the baseline or the post-baseline result is missing, the CFB and/or percentage CFB is set to missing as well.

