An adjusted expert-confirmed event rate will be computed for use in the determination of the 50%, 70%, and 90% responder endpoints comparing post-baseline event rates to baseline event rates. For the adjusted expert-confirmed event rate, the 2 additional requirements for confirmation of event rates used during screening will be applied to post-baseline expert-confirmed events to determine the number of confirmed events meeting the additional requirements. The additional requirements are:

- The events are unique, which is defined as an event that does not begin within 48 hours of the end of a previous event.
- The events must have either been treated, required medical attention or be documented to cause functional impairment based on subject entry in the diary. Functional impairment is defined as the subject being unable to perform their daily activities without restriction (ie, subject records that they are at least slightly restricted in their daily activities during their HAE event).

6.7.5.2. Number and Percentage of Subjects Who Are Event Free Over Entire Dosing Period and Effective Dosing Period

The following event-free endpoints will be derived for the entire dosing period and for the effective dosing period for Parts 1 and 2:

- The number and percentage of subjects with no confirmed events during the period of interest. Subjects with no confirmed events who discontinue before the end of the planned treatment period are not considered event-free.

The event-free rate for active treatment for subjects originally randomized to placebo will be based on the initial 24-week period during Part 2.

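### Change-from-baseline summaries of event rate set all confirmed on-treatment events against a more strictly counted baseline, so within-arm reductions are understated

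*SAP*

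**What the plan says.** **Baseline.** SAP 6.6.1 takes as numerator the "Number of HAE events meeting baseline criteria from Screening to First Dose Date/time" and refers to SAP 4.1 for the criteria. There, a qualifying event is one that "does not begin within 48 hours of the end of a previous angioedema event". SAP 4.1 also states: "The angioedema events must have either been treated, required medical attention, or have been documented to cause functional impairment". Swelling and expert confirmation are required as well.

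**On treatment.** Protocol 11.4.1.1 says: "After randomization through the end of Part 2, the expert will use their judgment to confirm or reject a reported event". Swelling is the only fixed requirement that remains. SAP 6.7.5.1 bases the confirmed event rate on all expert-confirmed events in the period.

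**Where the two are compared.** SAP 6.7.2 defines change as post-baseline minus baseline, and percent change as that difference over baseline. SAP 8.6.1 applies both to the monthly confirmed rate, in a summary "including CFB event rate and percentage CFB event rate by month". It also says: "A scatterplot will be produced for the difference between the baseline confirmed event rate and the confirmed event rate for Part 1", plotted against the baseline rate and repeated by gender. SAP 10.2 adds a plot of change in event rate against compliance. The figure list labels these outputs (14.2.2.5, 14.2.2.6, 14.2.2.7, 14.2.2.10) as using the expert-confirmed rate, not the adjusted one. The same holds for the plots that show baseline and on-treatment rates together (14.2.2.4, 14.2.2.8).

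**Where the SAP matches the definitions.** SAP 6.7.5.1 also defines an adjusted expert-confirmed rate, in which "the 2 additional requirements for confirmation of event rates used during screening will be applied" to post-baseline confirmed events. Its stated purpose is the 50%, 70% and 90% responder endpoints. Through SAP 6.7.5.4 and 8.8.2 it also feeds the Part 1 relative-reduction tables (14.2.6.1.1, 14.2.6.1.2) and the waterfall plot (14.2.6.2).

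**The concern.** A change from baseline is interpretable only if both sides count the same thing. Here the subtraction mixes a filtered count with an unfiltered one. The adjusted rate shows that the SAP recognises the problem, but section 8.6.1 does not use it for the monthly change columns or the change plots.

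The clinical study report could then give two different percent changes for the same subject against the same baseline: one in the relative-reduction tables and another implied by the change plots. With about 8 subjects per arm and power that the plan itself calls limited, readers will look closely at descriptive within-arm results, and these would understate any reduction.

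**Working it through.** **Inputs.** The definitions are those set out above. The share f of on-treatment confirmed events that would fail the two baseline rules is not in the documents; I assume 5% to 30%. The documents give no figure for the mismatch, so there is nothing of the plan's to reproduce on that. For an illustrative effect size I use Study 302 (Protocol 5.3.1): 1 − 1.31/2.35 = 44.3% and 1 − 1.65/2.35 = 29.8%, which match the stated 44% and 30%. Those are reductions against placebo, not against baseline, and serve here only as example values.

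**Direction.** The adjusted events are by construction a subset of the confirmed events. So the adjusted rate A and the confirmed rate C satisfy A = (1 − f) × C, with f ≥ 0.

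**Formula.** Let B be the baseline rate and s = A/B the like-for-like ratio.
- Like-for-like percent change: 100 × (s − 1).
- Planned percent change: 100 × (C/B − 1) = 100 × (s/(1 − f) − 1).

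**Results.** Planned percent change from baseline:

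| f (assumed) | no true change (s = 1) | true fall 21% (s = 0.79) | true fall 30% (s = 0.70) | true fall 44% (s = 0.56) |
|---|---|---|---|---|
| 5% | +5.3 | −16.8 | −26.3 | −41.1 |
| 10% | +11.1 | −12.2 | −22.2 | −37.8 |
| 20% | +25.0 | −1.2 | −12.5 | −30.0 |
| 30% | +42.9 | +12.9 | 0.0 | −20.0 |

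For example, 0.56/0.9 = 0.622, 0.56/0.8 = 0.70 and 0.56/0.7 = 0.80.

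**One subject, two answers.** A subject whose adjusted rate is exactly half of baseline is a 50% responder. At f = 20% the unadjusted comparison gives 0.5/0.8 = 0.625, a fall of only 37.5%.

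**Placebo.** Entry requires at least 2 qualifying run-in events, so regression to the mean pulls the on-treatment rate down while the mismatch pushes it up. I simulated this with gamma-Poisson counts: assumed shape 1, 2 or 4; assumed population mean 1.5, 2.0 or 2.5 per 28 days; entry with at least 2 events in 56 days; no drug effect. Across the nine settings:

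| f | change in the ratio of means | mean of individual percent changes |
|---|---|---|
| 0% | −14% to −5% | −4% to +9% |
| 10% | −4% to +6% | +7% to +21% |
| 20% | +8% to +19% | +20% to +36% |

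The sign depends on f, on the rate distribution and on how percent change is averaged. In Study 302 the placebo rate was 2.35 against a baseline of 2.98 pooled over arms: 2.35/2.98 − 1 = −21%. If the like-for-like fall were 21%, a net rise would need 0.79/(1 − f) > 1, that is f above 21%. This comparison is indicative only, because the baseline is pooled and the documents do not give Study 302's on-treatment confirmation rule.

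**Between arms.** With the same f in both arms, the ratio is [0.56/(1 − f)]/[1/(1 − f)] = 0.56, so the mismatch cancels.

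**The case against.** The strongest reply is that the matched measure already exists for Part 1 as a whole. The relative reduction in SAP 6.7.5.4 is minus the percent change on matched definitions. It is tabulated for the ITT and PP populations and plotted as a waterfall, and SAP 8.8.2 lists the confirmed events that drop out of the adjusted count, so a reader could gauge f. This stands. A reader who inferred that the adjusted rate serves the responder classification alone would be wrong. What remains unmatched is the monthly breakdown and the plots named above.

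Experts may merge several subject reports into one confirmed event (SAP 6.7.5.5), which may shrink the 48-hour part of the gap. That also stands, but merging is optional, has no 48-hour rule, and leaves the treatment-or-impairment rule untouched. Table shells are held in a separate document, so the absence of a warning footnote cannot be established.

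Two stronger readings are tempting. One is that within-arm change is the main measure carried into Part 2, where no placebo arm can offset the bias. The Part 2 endpoints (SAP 3.2.7) are the number and rate of events and the trend over time, and the plots that SAP 8.6.1 extends into Part 2 show mean rates. For subjects who switch from placebo, Protocol 13.4.4.2 summarises change from the placebo to the active period, both confirmed under the same post-randomisation rule. The other is that the primary analysis is biased. It compares arms on a common definition, with baseline only as a covariate.

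**Conclusion.** The point holds for the descriptive change-from-baseline outputs of SAP 8.6.1 and the compliance plot. The direction follows from the definitions alone: reductions can only be equal to or smaller than the like-for-like value. The size does not follow from the documents. It is a factor 1/(1 − f) on the ratio to baseline, so an illustrative 44% fall shows as 38%, 30% or 20% at an assumed f of 10%, 20% or 30%.

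A reader might infer that the placebo arm will show a spurious rise. Its change is biased upward, but the documents do not support a net rise as certain, since that depends on the unknown f and on regression to the mean. The primary between-arm estimate is unaffected by this route if f is equal across arms. The Part 1 responder, relative-reduction and waterfall outputs need no change.

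**What to change.** In SAP 6.7.5.1, extend the adjusted expert-confirmed rate to 28-day periods. Apply the two rules to each subject's continuous sequence of confirmed events, then assign events to months, so that a month boundary does not reset the 48-hour rule. In SAP 8.6.1 and 10.2, use the adjusted rate for every change and percent-change column and for the change and baseline-versus-on-treatment plots. Show the adjusted monthly rate beside the change columns so that they can be recalculated from the table.

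Keep the unadjusted confirmed rate for the primary model and the rate summaries. If any unadjusted change from baseline is still shown, footnote it as not like-for-like and refer to Table 14.2.6.1.1.

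The cost is minor programming and one extra set of columns. The rules are already specified for the Part 1 responder endpoints; only the by-month version is new. No new data are needed, and the primary test and its multiplicity control do not change.
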